In this double-blind research study, 66 participants will be randomized to receive real or sham tDCS prior to receiving an established interactive upper limb (shoulder/elbow and wrist) robotic training regimen. During the lead-in period, each subject will attend 3 weekly visits to complete TMS screening and have outcome measures (see below) assessed. Following the lead-in period, each subject will attend 36 90-minute sessions (3 visits/week) over a 12-week period (or up to 14-weeks to allow for missed appointments) comprising the training period. These visits will include further TMS screening and outcome measures, TMS, tDCS and robot training. Subjects will undergo further outcomes measures upon discharge and during a final 6-month follow-up visit. All study procedures will be administered and supervised by a therapist. All visits will be conducted in either the robot and TMS suites at the Feinstein Institute for Medical Research or at the Burke Medical Research Institute (Fig. 1). Participants will additionally undergo five blood draws longitudinally during the study to determine if cytokine levels change over the course of rehabilitation intervention, and if those changes are correlated with improved functional outcomes and treatment group (sham vs. real tDCS).

Lead-in Period

- Week 1, Visit 1 (approximately 30 minutes)
 - TMS screening questionnaire
 - Outcome measures
- Week 2 & 3, Visit 2 & 3 (approximately 60 minutes each)
 - Outcome measures
 - One time 10cc DNA sample and 2 separate 4cc baseline blood draws (2 total draws)

Training Period

- Week 4-15, Visits 4-39 (approximately 90 minutes)
 - TDCS risk questionnaire (visit 4 only)
 - TMS
 - tDCS
 - Robotic training
 - 4cc blood draw at midpoint, session 18 (1 total)
- Weeks 16 Visit 40 (approximately 2.5 hours)
 - tDCS

[figure not shown]

Fig 1: Diagram of study design showing the relationship between the robotic training program with or without tDCS and the evaluation schedule

- Robotic training
- Outcomes measures
- 4cc discharge blood draw (1 total)

Final Visit

- Week 40, Visit 41 (approximately 60 minutes)
 - Outcome measures
 - 4cc follow up blood draw (1 total)

Clinical Outcome Measures

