All outcome measures will be recorded three times prior to the training period separated by one week to ensure reliability and stability of measures, then again following the 12-week training program, and six months later. In general, study visits will take place at the institution of recruitment (e.g. subjects recruited through Feinstein will be treated at Feinstein). However, occasionally TMS and clinical assessments may take place at the other institute. Individual patient assessments will always be performed by the same evaluator to ensure internal consistency.

Fugl-Meyer (Primary): The Fugl-Meyer scale is a valid and reliable evaluation instrument used for measuring performance-based impairment in stroke patients (54, 55).

Medical Research Council motor power score (MRC): The MCR is a valid and reliable score that measures strength in isolated muscle groups of the involved shoulder and elbow on an ordinal scale (scale range: 0, no muscle contraction; 5, normal strength) .

Wolf Motor Function: The Wolf Motor Function Test is a valid and reliable assessment of upper extremity function by asking the patient to complete 15 motor-based tasks and two strength-based tasks (56).

Barthel Index (BI): The BI is a valid and reliable index of independence widely used in scoring improvement in the rehabilitation of stroke population (57). The BI consists of 10 items assigned various weightings: 15 points for the subcategories of walking and transfers; 10 points for the subcategories of feeding, bowel, bladder, toileting, dressing and stairs; 5 points for the subcategories of bathing and grooming. The BI is a cumulative score achieved by summing the score for all sections. The BI scores are recorded in multiples of 5, ranging from 0 (completely dependent) to 100 (independent in basic activities of daily living).

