Methods to address specific aim 1: We will compare demographic, clinical, kinematic, and tDCS variables between intervention groups using t-tests to compare means and chi-squared tests to compare proportions; where continuous data is non-parametric as defined by Shapiro-Wilk or Q-Q plots, we will use Kruskal Wallis tests. To assess the univariate relationship between treatment group and upper limb Fugl-Meyer score, repeated measures ANOVA will be used in order to account for longitudinal evaluations. Multivariate methods will include linear mixed models and ANCOVA to adjust for interactions or other covariates potentially contributing to the association between treatment and outcome. Further, Pearson correlation coefficients will be assessed to identify any linear association between kinematic, clinical and tDCS data points. The Spearman Rank correlation coefficient will be used for non-normally distributed variables. Like the Fugl-Meyer, secondary outcome measures, Wolf Motor Function, Barthel Index and Stroke Impact Scale are scored on a continuous scale and thus, will be analyzed as above. The MRC is scored on a scale from 0-5; Fisher analyses will be used to look for differences in strength between groups.

Specific Aim 2 (Kinematic): Determine if there is a statistically significant difference in a) mean speed, b) peak speed, c) smoothness, d) aim, and e) deviation from the straight line between subjects trained with and without tDCS prior to robotic training. This will be determined for both the trained tasks, as well as for the untrained, circle-drawing task. We will also include a static and dynamic quantitative measure of strength using the robotic device.

Methods to address specific aim 2: To assess the univariate relationship between treatment group and outcome, repeated measures ANOVA will be used in order to account for longitudinal evaluations. Multivariate methods will include linear mixed models and ANCOVA to adjust for interactions or other covariates potentially contributing to the association between treatment and outcome.

Specific Aim 3 (Neurophysiology): Determine if there is a statistically significant difference in: a) RMT, (b) MEP amplitude at 120% RMT, and c) SICI between subjects trained with and without tDCS prior to robotic training, both immediately following the training regimen, and 6 months later.

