Methods to address specific aim 3: To assess the univariate relationship between treatment group and outcome, repeated measures ANOVA will be used in order to account for longitudinal evaluations. Multivariate methods will include linear mixed models and ANCOVA to adjust for interactions or other covariates potentially contributing to the association between treatment and outcome.

POWER: Based on the previous study by Lo et al., we can expect twelve weeks of upper limb robotic training to result in a 2.88 change in the FM score (5). We estimated that tDCS plus robotics would result in a FM change score of 4.33. Using a two-sided alpha and a standard deviation of approximately 1.5, enrolling 56 subjects (28 per group) would give us 90% power to detect a difference in Fugl-Myer score of 1.45 between the intervention groups. To account for potential subject attrition, we aim to increase our sample size by 15% thus resulting in an enrollment goal to 66 (33 subjects per group).

Specific Aim 4 (Clinical): Determine if there is a statistically significant difference in the change in verbal expression scores on the Apraxia Battery for Adults (ABA-2) and Philadelphia Naming Test Short Form (PNT short form) between subjects with aphasia trained with and without tDCS prior to robotic training.

Methods to address specific aim 4: We will compare demographic, clinical, and tDCS variables between intervention groups with aphasia using t-tests to compare means and chi-squared tests to compare proportions; where continuous data is non-parametric as defined by Shapiro-Wilk or Q-Q plots, we will use Kruskal Wallis tests. To assess the univariate relationship between treatment group and ABA-2 score, repeated measures ANOVA will be used in order to account for longitudinal evaluations. Multivariate methods will include linear mixed models and ANCOVA to adjust for interactions or other covariates potentially contributing to the association between treatment and outcome. Further, Pearson correlation coefficients will be assessed to identify any linear association between clinical and tDCS data points. The Spearman Rank correlation coefficient will be used for non-normally distributed variables. Fisher analyses will be used to look for differences in strength between groups.

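### Aims 1–4 name repeated measures ANOVA for longitudinal outcomes with no sphericity correction or missed-visit rule; run classically, it can be anti-conservative and drops partly observed patients

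*Combined protocol and SAP*

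**What the plan says.** In Statistical Considerations and Data Analysis, the methods for Aim 1 state: "To assess the univariate relationship between treatment group and upper limb Fugl-Meyer score, repeated measures ANOVA will be used". The clause that gives the reason, "repeated measures ANOVA will be used in order to account for longitudinal evaluations", is repeated for the outcomes of Aims 2 and 3, and for Aim 4 the sentence reads "To assess the univariate relationship between treatment group and ABA-2 score, repeated measures ANOVA will be used".

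Each time, the next sentence adds: "Multivariate methods will include linear mixed models and ANCOVA to adjust for interactions or other covariates potentially contributing to the association between treatment and outcome". Mixed models are therefore in the plan, but their stated job is adjustment. They are not assigned to repeated or missed visits, and no ranking against the ANOVA is given.

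On timing, Clinical Outcome Measures says "All outcome measures will be recorded three times prior to the training period separated by one week", then once after the training programme and once six months later. Visit Schedule places these at weeks 1, 2 and 3, week 16 and week 40.

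On attrition, the POWER paragraph says "To account for potential subject attrition, we aim to increase our sample size by 15" per cent, which takes 56 patients to 66.

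For Aims 1–4 the documents do not say which model is primary, how the three lead-in scores enter, what covariance is assumed, whether a sphericity correction applies, or what happens to a patient with a missed evaluation. Blood Sampling does have such a rule: the samples that were collected are analysed.

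**The concern.** Classical repeated measures ANOVA has two properties that fit this schedule poorly.

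First, its within-patient F test assumes that the difference between any two visits has the same variance. Here three scores lie a week apart before treatment, and the other two follow 13 and 24 weeks later. Differences among the lead-in scores may well vary less than changes over training or follow-up. If they do, and no correction is applied, the arm-by-time test rejects too often.

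Second, it uses complete records only. A patient assessed at discharge who does not return at six months leaves the analysis, and the observed discharge score leaves too. If return is related to how much the patient gained, the remaining patients give a distorted treatment difference.

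The two problems act differently. The first inflates false positives. The second, when patients with small gains are the ones lost under one rule in both arms, dilutes a true effect.

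**Working it through.** **1. The plan's own figures.** Inputs from POWER: changes of 2.88 and 4.33 (difference 1.45), SD 1.5, 90% power, 28 per group. The alpha level is not stated; 0.05 two-sided is assumed.
- n per arm = 2(1.960 + 1.282)² × 1.5² / 1.45² = 2 × 10.51 × 2.25 / 2.1025 = 22.5, so 23 (24 with the t distribution). With 28 per arm, power is 95.1% (94.4% by t). The 28 at 90% corresponds to an alpha of about 0.02–0.025. This is a separate matter and errs towards more patients.
- 56 / (1 − 0.15) = 65.9, so 66. The attrition step reproduces.

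**2. Are the visit differences equally variable?** Take a stable lead-in with error SD s. Fix the SD of change from the lead-in mean at the plan's 1.5, and assume that true gains at discharge and six months correlate 0.7. The true-gain variance is v = 1.5² − s² − s²/3.
- s = 0.5: v = 2.25 − 0.25 − 0.083 = 1.917. Variance of the difference between two lead-in scores: 2s² = 0.50. Discharge minus one lead-in score: v + 2s² = 2.42. Six months minus discharge: 2v(1 − 0.7) + 2s² = 1.65. These are clearly unequal.
- s = 1.0: v = 0.917, and the same three variances are 2.00, 2.92 and 2.55. These are nearly equal.

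So the size of the problem depends on s, which the documents do not give.

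**3. Type I error of the arm-by-time F test.** Simulation with 28 per arm, five visits and 40,000 runs. F is referred to 4 and 4 × 54 = 216 degrees of freedom. Departure from sphericity is ε = (tr D)² / [4 tr(D²)], with D the double-centred covariance matrix; ε = 1 means sphericity holds. The Greenhouse–Geisser correction multiplies both degrees of freedom by the estimated ε.

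| Assumed covariance | ε | Uncorrected | Greenhouse–Geisser |
|---|---|---|---|
| Equal correlations | 1.00 | 5.1% | 4.6% |
| Exponential decay, correlation 0.4–0.9 at 24 weeks | 0.40–0.48 | 9.4–10.2% | 4.8–5.1% |
| Decay plus 5–10% measurement error | 0.56–0.68 | 7.1–8.0% | 4.8% |
| Stable lead-in, s = 0.5 | 0.55 | 8.2% | 4.8% |
| Stable lead-in, s = 0.75 | 0.74 | 6.6% | 4.8% |
| Stable lead-in, s = 1.0 | 0.92 | 5.2% | 4.4% |

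With s = 0.3, other runs gave 9.0–9.5% uncorrected.

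**4. If the three lead-in scores are averaged** (three time levels), the uncorrected error is 5.8–6.1% under exponential decay and about 5% with a stable lead-in and correlation 0.7. Across the range examined it is about 4.5–6.6%. A boundary case, with true gains at discharge and six months perfectly correlated and s = 0.3, reaches about 8.5%.

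**5. How many patients a complete-record analysis keeps.** With 15% loss, 66 × 0.85 = 56, the planned number. If instead each of five evaluations is missed independently with probability q (assumed), 66(1 − q)⁵ remain: 57 for q = 3%, 51 for 5%, 39 for 10%. Power for the 1.45-point difference is then about 93% at q = 5% and 85% at q = 10%.

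**6. Bias in the completers' discharge difference.** True difference 1.45, 33 per arm, change SD 1.5, about 15% missing at six months.

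| Loss at six months | Difference among completers |
|---|---|
| Completely at random | 1.45 |
| Small gains lost more, same rule in both arms, log-odds slope 0.5 per point | 1.36 |
| Same, slope 1 | 1.23–1.25 |
| Same, slope 2 | 1.08–1.10 |
| Rule differs by arm (two versions) | 1.01–1.12 |
| No true effect, same rule | 0.00 |
| No true effect, rule differs by arm (one version) | −0.34 |

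Power of a t test on the completers' discharge change is about 93%, 90% and 86% for slopes 0.5, 1 and 2, against about 97% with all 66. A likelihood-based estimate of the six-month difference stayed at 1.45 (0.00 under the null) in every scenario where loss depended only on observed gain.

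**The case against.** The strongest reply is that the plan does not commit to the faulty analysis. It calls the ANOVA the univariate assessment, names mixed models in the next sentence, and ranks nothing. A reader might infer that the ANOVA is the primary analysis, that incomplete patients will be discarded, and that the test will go uncorrected. None of the three is stated. The latter two are properties of the classical implementation. This stands, and it is why the point is conditional.

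It also stands that the 9–10% error needs all five visits as separate levels and an omnibus interaction test. Averaging the lead-in scores removes most of it. A single pre-post change, which is what the power calculation concerns, has no sphericity assumption. At s = 1.0 the inflation is negligible.

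On missing visits, a reader might infer that the trial becomes underpowered or biased. The 15% allowance already covers a loss of that size. There is no bias when loss is completely at random, nor under the null when one rule governs both arms. Power falls clearly below the stated 90% only at slope 2, an odds ratio of e² = 7.4 per point, which is steep. The power figures in step 6 are for a comparison of completers' discharge changes, not for the ANOVA interaction test.

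Finally, the five-visit schedule is clearly documented only for the clinical scales. Visit Schedule lists no TMS at the discharge or final visit, the kinematic measures are not among the Clinical Outcome Measures, and the WAB-R is given three times. The figures above should not be carried over to Aims 2 and 3 or to the WAB-R.

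What does not fall away is that the ANOVA is the only method the plan ties to the Fugl-Meyer and ABA-2 by name, and the only one it says accounts for the longitudinal data. None of the safeguards just described is written down.

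**Conclusion.** The point holds in conditional form. For Aims 1–4 the plan gives the longitudinal task to repeated measures ANOVA and leaves out both a sphericity correction and a rule for missed evaluations.

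- **Type I error.** If the classical form is applied to the five clinical evaluations, the arm-by-time error is about 5–10% against an assumed 5%, and about 4.5–6.6% with averaged lead-in scores outside the boundary case. This rests on assumed covariance structures.
- **Missed evaluations.** Complete-record analysis discards observed discharge scores. Where six-month loss depends on discharge gain under one rule in both arms, the discharge difference shrinks from 1.45 to about 1.36–1.09. This rests on assumed slopes of 0.5–2.

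The documents do not support saying that the error rate is above nominal, that the estimate is biased, or that the sample is too small. They support saying that the named method permits the first two and that a better one is already listed.

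**What to change.** For the repeated outcomes of Aims 1–4, make the linear mixed model the stated analysis:
- fit it to all observed evaluations of all randomised patients;
- treat visit as a category, with arm-by-visit terms, using the visits at which each outcome is actually measured;
- use an unstructured covariance (5 × 6 / 2 = 15 parameters for five visits) with Kenward–Roger degrees of freedom;
- state that the analysis assumes missingness depends only on observed data.

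Keep any repeated measures ANOVA as supportive only, with the Greenhouse–Geisser correction and a count of the patients it omits, by arm.

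The cost is a change of wording in the analysis section. The model is already named, no new data are needed, and enrolment stays at 66. The model does not protect against loss that depends on unobserved outcomes.

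### The ordinal MRC strength score gets only a Fisher test: valid, but inefficient when three lead-in scores and two later visits are recorded

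*Combined protocol and SAP*

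**What the plan says.** Clinical Outcome Measures describes the MRC as a score that "measures strength in isolated muscle groups of the involved shoulder and elbow on an ordinal scale", graded 0 to 5. The same section sets the schedule for every outcome: "All outcome measures will be recorded three times prior to the training period separated by one week", "then again following the 12-week training program, and six months later". Each patient should therefore have five MRC assessments, three of them before treatment.

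Under Methods to address specific aim 1, the Fugl-Meyer is handled longitudinally: "repeated measures ANOVA will be used in order to account for longitudinal evaluations". Mixed models and ANCOVA are listed for covariate adjustment. The other secondary scales follow the same route: "Wolf Motor Function, Barthel Index and Stroke Impact Scale are scored on a continuous scale and thus, will be analyzed as above". MRC does not: "The MRC is scored on a scale from 0-5; Fisher analyses will be used to look for differences in strength between groups". The plan does not state the visit, whether the raw grade or its change is tabulated, how grades are grouped, how muscle groups are combined, or how the lead-in scores enter.

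The last sentence of Methods to address specific aim 4 repeats it: "Fisher analyses will be used to look for differences in strength between groups". Aim 4 concerns verbal expression, and neither its statement nor its methods name a strength outcome.

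**The concern.** The plan's implied reason for separating MRC is that it is not continuous. That argues for a rank or ordinal method, not a nominal one. The Fisher test for a table with several columns (Freeman-Halton) gives the same p-value however the grades are relabelled, so a shift from 2 to 3 counts no differently from a shift between any other two grades. It also takes one observation per patient and has no place for a covariate.

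Entry is wide (Fugl-Meyer 7 to 58), so patients are likely to differ a good deal in strength before treatment. The three lead-in assessments are the natural means of removing that spread. At stake is the precision of the strength comparison, an outcome type that featured in the pilot results supporting the trial.

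**Working it through.** **The plan's own figure.** No power is stated for MRC. The only sample size calculation is for Fugl-Meyer: difference 4.33 − 2.88 = 1.45, "Using a two-sided alpha and a standard deviation of approximately 1.5". The alpha value is not given. At 0.05, n per arm = 2(1.960 + 1.282)² / (1.45/1.5)² = 2 × 10.51 / 0.934 = 22.5, so 23. The stated 28 gives about 95% power rather than 90%, which is conservative and has no bearing on MRC. I use 28 per arm below.

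**What baseline adjustment is worth.** Let ρ be the correlation between any two visits. The squared correlation of a post-training score with the mean of three lead-in scores is 3ρ²/(1 + 2ρ). The variance left after adjustment, as a share of the unadjusted variance, is:
- ρ = 0.6: 1 − 1.08/2.2 = 0.51
- ρ = 0.8: 1 − 1.92/2.6 = 0.26
- ρ = 0.9: 1 − 2.43/2.8 = 0.13

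**Simulation 1 (assumed inputs).** Grade = a latent normal with mean 2.7 and total SD 1, rounded and clipped to 0-5; 28 per arm; two-sided 0.05; 1,000 runs per setting. The effect of 0.42 grade is pilot-sized: (22 − 19.5)/6 = 0.42, if the pilot score out of 30 is six 0-5 items. That is an assumption. The pilot had 4 real and 2 sham patients and measured the wrist.

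| Effect (grades) | ρ | Fisher, post grades | Rank test, post grades | Fisher, improved ≥1 | Fisher, change | ANCOVA, lead-in mean, one post visit | ANCOVA, both post visits |
|---|---|---|---|---|---|---|---|
| 0.42 | 0.6 | 16% | 30% | 17% | 19% | 51% | 74% |
| 0.42 | 0.8 | 16% | 30% | 32% | 35% | 75% | 89% |
| 0.42 | 0.9 | 16% | 30% | 45% | 54% | 86% | 97% |
| 0.97 | 0.6-0.9 | 70-74% | 91-93% | 77-100% | 78-100% | 99-100% | 100% |
| 1.2 | 0.6-0.9 | 91-92% | 98-99% | 90-100% | 90-100% | 100% | 100% |

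The step from Fisher to the rank test on the same grades (16% to 30%) is the cost of ignoring order. The further step to ANCOVA is the gain from the lead-in scores.

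With no effect, Fisher on post grades rejects in 4-6% of runs, Fisher on improvement in 2-3%, and ANCOVA in about 5%. All are valid to within simulation error.

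**Simulation 2 (planned effect carried over).** The Fugl-Meyer effect is 1.45/1.5 = 0.967 SD of change. With total SD 1, that is 0.967 × √(2(1 − ρ)) grades: 0.865, 0.749, 0.612 and 0.432 for ρ = 0.6, 0.7, 0.8 and 0.9. Over those four values, power is:
- Fisher on post grades: 60%, 49%, 32%, 15%
- Fisher on improvement: 66%, 64%, 59%, 50%
- Fisher on change: 66%, 68%, 63%, 57%
- ANCOVA with one post visit: 97%, 97%, 95%, 89%

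**Simulation 3 (variance components varied).** Between-patient SD 0.7-1.0, visit error SD 0.35-0.6, effect 0.42-0.5 grade. The implied ρ runs from 0.49/(0.49 + 0.36) = 0.58 to 1/(1 + 0.1225) = 0.89. Power is roughly 12-34% for Fisher on post grades, 14-60% for Fisher on improvement and 50-96% for ANCOVA on the lead-in mean. The ends of these ranges move by a few points with the assumed mean grade.

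**The case against.** The best defence is that the sentence does not say what is tabulated. Aim 1 is framed as a comparison of change, so a table of improved against not improved is a natural reading, and that table does use a baseline score. This stands: a reader might infer that the lead-in scores are ignored outright, but the documents do not settle it. The improvement and change readings are therefore shown above. They do better than post-only grades in most settings, yet still fall well short of the adjusted model at modest effects.

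A reader might also infer that a real strength effect would very probably be missed. That does not follow. It depends on an effect size and correlation the documents do not give for MRC; at a shift near one grade, Fisher on post grades already succeeds in 70% or more of runs.

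Nor would a null MRC result reflect only the test. Randomisation keeps Fisher valid, and a null could mean no effect. Strength is also captured by robot measurement under Aim 2 (with longitudinal methods), two Wolf tasks and a Stroke Impact Scale domain.

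Finally, one might picture a summed score out of 30 spread over a sparse table. That score is the pilot's wrist measure. The trial's MRC covers shoulder and elbow, and nothing says grades are summed, so no figures for that case are offered.

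MRC is also absent from the outcomes named in Specific Aim 1, which limits the weight of the point.

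**Conclusion.** The concern holds as one of efficiency and specification, not validity. MRC is the one Aim 1 clinical scale kept from the longitudinal and covariate-adjusted methods, and the chosen test discards order and, at best, most of the repeated measurement. For an effect of about half a grade, the adjusted model has clearly more power than Fisher on any reading examined. For effects around one grade or more the gap narrows and can nearly close.

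The direction is consistent across every non-null setting where power is not already near 100%. The exact percentages rest on assumed grade distributions, effects and visit correlations, and on treating MRC as a single 0-5 score. This is a change the plan should make; it does not threaten the primary Fugl-Meyer analysis.

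**What to change.** Replace the Fisher sentence under Aim 1 with a baseline-adjusted analysis of MRC:
- State which shoulder and elbow muscle groups are graded and how they are combined into the analysed score.
- Use the mean of the three lead-in scores as baseline.
- Analyse both later visits with the mixed model or ANCOVA already listed, naming which visit gives the main comparison.
- Support it with a proportional-odds or rank analysis.

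The small downside is that a linear model treats grades as equally spaced; the ordinal analysis checks whether that matters.

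Delete the repeated Fisher sentence from the Aim 4 methods, or name the outcome it is meant for.

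The cost is wording only. The schedule already collects all five assessments, so no new data or visits are needed. The change should be made before the treatment code is revealed.

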In patients with chronic stroke (>6months post-injury, stable unilateral motor deficit) using a within-subjects repeated-measures design we will evaluate the effects of 12 weeks of robotic upper limb training (3x/week, 36 sessions, shoulder/elbow/wrist in alternating sessions) with real or sham tDCS before the robotic training. Functional improvement will be determined by a change in upper-limb Fugl-Meyer (primary), Wolf Motor Function Test, Barthel Index, and Stroke Impact Scale (secondary) outcome measures following the training, and assessed again six months later.

SPECIFIC AIM 2: To identify and compare kinematic performance characteristics between intervention groups.

Quantitative measurements obtained from robotics are highly sensitive, precise and reliable. These data will provide important contributions to understanding the components of motor control that underlie improvements in clinical function. Previously published studies and new pilot data from our group support the hypothesis that a relationship may exist for five key parameters (mean speed, peak speed, smoothness, aim, deviation) (50), however confirmation in a larger number of patients needs to be established. This information may additionally be useful as a clinical predictor of motor recovery. Since movement smoothness was shown to improve with just one session of tDCS and robotics, we predict that there will be a strong and sustained effect on this parameter. Movement smoothness is associated with more

advanced stages of motor learning, and has high correlation with functional clinical scales, and as such should be mirrored with change in Fugl-Meyer score.

SPECIFIC AIM 3: To identify and compare the neurophysiological characteristics between intervention groups.

The relationship between clinical improvement and neurophysiological measures pertaining to robotic motor training following stroke are presently not described in the literature. By measuring accepted, quantitative and reliable EMG response (wrist and elbow flexor/extensor muscles) to TMS (cortical inhibition and excitation) we will establish: (i) the plasticity associated with training, and (ii) the neurophysiological characteristics of patients (and muscles within patients) who respond to training. By understanding how brain excitability changes underpin motor dysfunction, and motor recovery, interventions can be more effectively prescribed and prognoses established.

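### Aim 3 seeks significant real-versus-sham differences in three TMS measures at two times, with no lead contrast, order, adjustment or exploratory label

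*Combined protocol and SAP*

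**What the plan says.** All references are to the combined protocol and SAP.

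- **Statistical Considerations and Data Analysis, Specific Aim 3.** The task is: "Determine if there is a statistically significant difference in: a) RMT, (b) MEP amplitude at 120% RMT, and c) SICI". The comparison is real versus sham tDCS, which the plan words as "between subjects trained with and without tDCS prior to robotic training, both immediately following the training regimen, and 6 months later".
- **The methods paragraph for that aim.** The main analysis is stated thus: "To assess the univariate relationship between treatment group and outcome, repeated measures ANOVA will be used in order to account for longitudinal evaluations". Linear mixed models and ANCOVA follow as multivariate methods. Nothing says which analysis decides, or whether each visit gets its own test.
- **TMS Evaluation, Resting Motor Threshold.** MEP amplitude is to be examined for change at each time point. The muscle described is the right flexor carpi radialis (FCR).
- **Other aims.** For Aim 1: "Functional improvement will be determined by a change in upper-limb Fugl-Meyer (primary"). Aim 4 names the Apraxia Battery for Adults as primary. Aim 5 is described as a pilot with mainly descriptive analysis. Aim 3 has neither kind of statement.
- **POWER.** The sample size rests on Fugl-Meyer alone, and the test level appears only as "Using a two-sided alpha and a standard deviation of approximately 1.5", with no number.

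**The concern.** Three measures at two times give up to six real-versus-sham comparisons of equal standing, each framed as a search for significance. Any one of them reaching nominal significance could be reported as the neurophysiological effect of tDCS. If Fugl-Meyer is positive, a chance TMS finding could be offered as its mechanism. If Fugl-Meyer is null, the same finding could be offered as evidence that tDCS did something. With no lead fixed in advance, a reader of the results cannot tell a planned finding from the best of several.

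**Working it through.** **Plan's own figure.** The documents state no error rate for Aim 3, so there is none to reproduce. The only test-level information is in the power statement, which does not reveal the alpha. With 28 per group, difference 1.45, SD 1.5 and an assumed two-sided 0.05:

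- standardised difference = 1.45 / (1.5 × √(2/28)) = 3.617
- power = Φ(3.617 − 1.960) = 95.1%, against the stated 90%

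The stated 90% would fit an alpha near 0.02 to 0.025, or an SD of about 1.64 to 1.67 at 0.05. The level must therefore be assumed.

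**Inputs**

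| Input | Value | Source |
|---|---|---|
| Measures | 3 (RMT, MEP amplitude, SICI) | Aim 3 statement |
| Times | 2 (after training, 6 months later) | Aim 3 statement |
| Tests | 6 if visits are tested separately; 3 if there is one group test per measure | two readings of the Aim 3 statement and methods |
| Level per test | two-sided 0.05 | assumption |
| Correlation between test statistics | 0 to 0.8, common to all pairs | assumption |

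**Independent tests.** The chance of at least one false positive among k tests is 1 − (1 − 0.05)^k.

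- k = 6: 1 − 0.95^6 = 26.5%
- k = 3: 1 − 0.95^3 = 14.3%

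**Correlated tests.** Correlated two-sided z-tests were simulated with no true effect.

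| Correlation | 6 tests | 3 tests |
|---|---|---|
| 0 | 26.5% | 14.3% |
| 0.5 | 20.7% | 12.5% |
| 0.8 | 13.9% | 9.8% |

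Two-sample t-tests with 28 per arm give nearly the same values (six tests: 26%, 21% and 14%). Letting the between-measure and between-visit correlations differ stays inside this range; for example, 0.5 between measures and 0.6 between visits gives 21.4%.

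**After a fix**

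- One lead contrast carrying the only significance claim: 5%.
- Holm over all six: with no true effect, a false claim needs the smallest p-value below 0.05/6 = 0.0083. The rate is 1 − (1 − 0.0083)^6 = 4.9% if independent, and lower if correlated.
- Lead at 0.05 with the other five as a separate Holm family: 1 − 0.95 × (1 − 0.01)^5 = 9.7% if independent. This holds 5% overall only if the five are tested after the lead succeeds.

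**The case against.** The strongest reply is that Aim 3 is mechanistic and subordinate. Fugl-Meyer is primary and is the only outcome with a power calculation, so no TMS result can change the trial's main conclusion. Whether such measures need family-wise control is partly a matter of taste. The introduction presents TMS as a way to characterise and measure motor performance better. All this stands and limits the weight of the point. It does not supply the missing label: the Aim 3 statement still asks for statistical significance, and the plan does call Aim 5 descriptive.

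A second reply is that the named analysis may involve only three tests, because "repeated measures ANOVA will be used in order to account for longitudinal evaluations" can be read as one model per measure covering both visits. That reading is open. So is the six-test reading, since the aim names both times and the RMT text looks for change at each one. Both are therefore carried through, and even three tests give about twice the nominal rate or more.

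Three stronger inferences are tempting but not supported:

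- **A flat 21%.** This needs alpha 0.05, separate visit tests and a correlation of 0.5. The plan states none of these.
- **Up to 24 tests across four muscles.** The Specific Aims text does mention "EMG response (wrist and elbow flexor/extensor muscles) to TMS (cortical inhibition and excitation) we will establish: (i) the plasticity associated with training", but TMS Evaluation describes recording from FCR only, and the Aim 3 analysis statement lists no muscles.
- **A confirmatory promise in that same sentence.** What it says the trial will establish concerns plasticity with training and the features of patients who respond. Neither is a real-versus-sham claim.

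**Conclusion.** The point holds for Aim 3's neurophysiological claims. The aim sets out to find significance across three measures and two times without a lead, order, adjustment or exploratory label, although the plan gives a lead or a descriptive label in Aims 1, 4 and 5. At an assumed two-sided 0.05 and correlations from 0 to 0.8, the chance of at least one false claim if tDCS has no effect is about 14% to 26% with visits tested separately, and about 10% to 14% with one test per measure. That is about 2 to 5 times the assumed level. A lower alpha would reduce these figures; reading the mixed-model and ANCOVA results as further chances would raise them. The Fugl-Meyer conclusion is untouched, so this is a worthwhile, inexpensive improvement and not a threat to the trial.

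**What to change.** Amend the Aim 3 statement before unblinding, state the numeric alpha, and adopt one of two options.

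1. **Name one lead contrast**, meaning one measure at one visit with one deciding analysis. An example is real versus sham on change in FCR MEP amplitude at 120% RMT, from the pre-training TMS baseline to the end of training. The investigators should choose; RMT has its own rationale in the protocol. Holm-adjust the remaining contrasts, and say whether they are tested only if the lead succeeds, since that determines whether the overall rate is 5% or up to about 10%.
2. **Label Aim 3 exploratory.** Report estimates with confidence intervals for all contrasts and make no significance claim.

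If FCR MEP amplitude is the lead, two points need settling first:

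- Confirm that TMS is recorded before training, after training and at 6 months. The Visit Schedule itemises TMS only for visits 4 to 39. The lead-in lists a screening questionnaire and outcome measures, and visits 40 and 41 list no TMS. The study diagram, which is not reproduced here, may cover this.
- Reconcile the right FCR named in TMS Evaluation with stimulation of the affected hemisphere, because the two conflict for a patient with left hemiparesis.

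The cost is statistical wording, with no extra patients. No extra data are needed if the recordings are confirmed. The downside is that TMS results other than the lead need stronger evidence or lose their significance claim.
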